5.3 APPENDIX 3 DEMOGRAPHICS AND BASELINE CHARACTERISTICS, PRIOR OR CONCOMITANT MEDICATIONS

The following demographics and baseline characteristics, medical and surgical history and disease characteristics will be summarized using descriptive statistics in the randomized population.

Demographic and baseline characteristics

- Gender (Male, Female).
- Age in years (quantitative and categorical variable: Children (2-11 years), Adolescents (12-17 years), 18 to <65, 65 to <85 and ≥85 years), the two first categories are applicable only to participants in the secondary population.
- Race (White, Black or African American, Asian, American Indian or Alaska Native, Native Hawaiian or other Pacific Island, other).
- Ethnicity (Hispanic, non-Hispanic).
- Weight in kilograms (quantitative and categorical variable: 10 to <15, 15 to <30, 30 to <50, 50 to <100, ≥100).
- Body mass index (BMI) in kg/m² (quantitative and categorical variable: <18.5, 18.5 to <25, 25 to <30, ≥30).

Randomization strata

The randomization strata is only applicable for primary population. The two categories will be presented: able to walk, unable to walk.

Disease characteristics

The time since diagnosis and time since symptom onset will be derived from the subtraction between two years: year of randomization and year of diagnosis or symptom onset. A value of zero means that diagnosis or symptom were occurred the year of randomization.

Based on the same principle, the age at diagnosis and age at symptom onset will be derived from the difference between the year of diagnosis or symptom onset and the year of birth.

Medical or surgical history

Medical (or surgical) history includes previous relevant medical and surgery history collected at baseline. Medical and surgical history will be coded to a LLT, PT, HLT, HLGT, and associated to

a primary SOC using the MedDRA version currently in effect at Sanofi at the time of database lock.

Medical/ surgical history will be summarized in each treatment arm by primary SOC and PT. Events will be sorted by SOC internationally agreed order and decreasing frequency of PT based on the incidence in the primary population.

Alcohol habits at baseline

Alcohol habits include:

- Frequency of alcoholic drinks in the last 12 months (Never/Occasional/At least monthly/At least weekly/At least daily).
- Number of standard drinks (1 or 2/Greater than 2, where standard drink means 1 pint/bottle of beer, 1 glass of wine, 1 shot of hard liquor...) per day when drinking alcohol.

Prior or concomitant medications

All medications will be coded using the World Health Organization-Drug Dictionary (WHO-DD) using the version currently in effect at Sanofi at the time of database lock:

- Prior medications are those the participant used prior to first IMP intake. Prior medications can be discontinued before first administration or can be ongoing during treatment period.
- Concomitant medications are any medications received by the participant concomitantly to the IMP during the on-treatment period.
- Post-treatment medications are those the participant took in the period running from the end of the concomitant medications period up to the end of the study.
- A given medication can be classified as a prior medication and/or as a concomitant medication and/or as post-treatment medication. If it cannot be determined whether a given medication was taken prior or concomitantly or post, it will be considered as prior, concomitant, and post-treatment medication.

The prior and concomitant medications will be summarized for the randomized and exposed population, by anatomic and therapeutic level. The summaries for prior medications will be sorted by decreasing frequency of anatomic category (ATC) based on the overall incidence across study intervention group. The summaries for concomitant medications will be sorted by decreasing frequency of ATC based on the incidence in the venglustat group of the primary population. In case of equal frequency, alphabetical order will be used.

Participants will be counted once in each ATC category (anatomic or therapeutic).

5.4 APPENDIX 4 DATA HANDLING CONVENTIONS

General conventions

The following formulas will be used for computation of parameters.

Demographic formulas

- $$\text{BMI} = \frac{\text{weight(kg)}}{\text{height(m)}^2}$$

Missing data for primary/secondary efficacy endpoints

The primary analysis will include all data collected in participants from the primary population, regardless of whether or not participants completed the treatment period. Participants who prematurely and permanently discontinue study medication will be requested to continue to be assessed after treatment discontinuation, up to the Week 104 visit. Data collected after treatment discontinuation will be included in the primary analysis. All efforts will be made to minimize the amount of missing data.

The linear mixed effect model described in [Section 3.2.2.2](#) will be run on all observed data, including data collected after treatment discontinuation. Missing data will be handled by the model assuming a Missing At Random mechanism.

Due to the small sample size in this study, it is expected that a model-based imputation of missing data will not be feasible. In particular, imputation of missing data based on a model estimated from participants from the same treatment arm who discontinued the study treatment but continued to have their data collected will likely be unfeasible, due to the small number of participants in this category.

Age for children/adolescents participants for derivation of PCSA

For children/adolescents participants, the PCSA definition depends on the category of age. Therefore, it is necessary to derive the age during the study. For this purpose, the age during the study will be defined as the age at screening plus the time (in years) since randomization.

Analysis windows for time points

For all analyses, D1 will be defined as the reference date of the participant. For treated participant, the reference date will be the day of first IMP intake. For the other participants, randomized but not treated the reference date will be the day of randomization.

For endpoints not collected at each visit (CSF biomarkers, neurological examination), analysis by time points will be summarized using the protocol planned visits.

For other endpoints collected at multiple visits, the following analysis windows (see [Table 13](#)) will decide how the scheduled and/or unscheduled visits will be used in the by-visit analyses of efficacy data, laboratory safety data, vital signs, ophthalmological examination, patient reported outcome variables as well as PK variables.

A measurement (scheduled or unscheduled) will be used if it is available and measurement date is within the analysis window.

After applying these time windows, if multiple assessments are associated to the same time point, the value collected at the scheduled visit will be used, if any. Otherwise, the closest from the targeted study day will be used. If the difference is a tie, the value after the targeted study day will be used. For all endpoints except PK, if multiple valid values exist within a same day, then the first value of the day will be selected.

If there is no measurement for a given parameter in an analysis window, data will be considered missing for the corresponding visit. For laboratory data, only central measurements will be taken into account by default. Nevertheless, due to COVID-19 situation, in case of high number of missing central assessments by analysis window, local assessments may be taken into account.

Table 13 - Analyses window definition

Time point	Targeted study day	Analysis window in study days
Week 12	D84	D2 - D133
Week 26	D182	D134 - D273
Week 52	D364	D274 to D455
Week 78	D546	D456 to D637
Week 104	D728	D638 to D819
Week 130	D910	D820 to D1001
Week 156	D1092	D1002 to D1183
Week 182	D1274	D1184 to D1365
Week 208	D1456	D1366 to D1547

Table 14 - Analyses window definition for PK analyses

Time point	Target study day	Analysis window
Day 1/ Pre dose*	Day 1 / Pre dose	Before Day 1 dose
Day 1/ 1 st Post dose*	Day 1 / 0.5 hours Post dose	20 min to 40 min after Day 1 dose
Day 1/ 2 nd Post dose	Day 1 / 3 hours Post dose	2 h to 4 h after Day 1 dose
Day 1/ 3 rd Post dose*	Day 1 / 8 hours Post dose	6 h 45 to 9 h 15 after Day 1 dose
Day 1/ 4 th Post dose*	Day 1 / 12 hours Post dose	10 h to 14 h after Day 1 dose
Day 1/ 5 th Post dose*	Day 1 / 24 hours Post dose	20 h to 28 h after Day 1 dose
Week 12/ Pre dose	Week 12 / Pre dose	Before Week 12 dose
Week 12/ 1 st Post dose	Week 12 / 0.5 hours Post dose	20 min to 40 min after Week 12 dose
Week 12/ 2 nd Post dose	Week 12 / 3 hours Post dose	2 h to 4 h after Week 12 dose
Week 12/ 3 rd Post dose	Week 12 / 8 hours Post dose	6 h 45 to 9 h 15 after Week 12 dose
Week 12/ 4 th Post dose	Week 12 / 12 hours Post dose	10 h to 14 h after Week 12 dose
Week 12/ 5 th Post dose	Week 12 / 24 hours post dose	20 h to 28 h after Week 12 dose
Week 26/ Pre-dose	Week 26 / Pre-dose	Before Week 26 dose
Week 26/ Post dose	Week 26 / 3 hours post dose	2 h to 4 h after Week 26 dose

Time point	Target study day	Analysis window
Week 52 / Pre-dose	Week 52 / Pre-dose	Before Week 52 dose
Week 52/ Post dose	Week 52 / 3 hours post dose	2 h to 4 h after Week 52 dose
Week 104 / Pre-dose	Week 104 / Pre-dose	Before Week 104 dose

*Time points only applicable for participants included in PK sub-study

Unscheduled visits

Unscheduled visit measurements will be used for computation of baseline, the last on-treatment value and worst on-treatment value. For parameters summarized according to analysis time windows, unscheduled visit measurements may also be used to provide a measurement for a timepoint.

For laboratory data, vital signs and ECG analysis unscheduled visit measurements will be used to provide the analysis according to the PCSA and the shift summaries for safety.

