3. Period 3 (104-week OLE period): Participants in both the primary and secondary population will be automatically entered into the OLE period following completion of primary analysis period (period 2). All participants will receive venglustat for 104 weeks in an open-label design. Long-term safety, tolerability, PD, and efficacy of venglustat once daily administration will be assessed during the 104-week treatment period. Participants who complete the primary analysis period but would not continue to OLE period, and safety follow up /end of study (EOS) visit will be conducted 6 weeks after the W104 visit. Participants who complete the primary analysis period within 3 months prior to the OLE (amended protocol 4) approval by local regulations, will have the option to enroll into the OLE when the OLE (amended protocol 4) is approved. Participants who prematurely discontinue the study treatment from the primary analysis period will not have the option to enroll into the OLE.
4. Period 4 (post-treatment safety observation period, 6-week follow-up period). The post-treatment safety observation period will be for 6 weeks after Period 3, and safety and tolerability will continue to be assessed.

Post-trial access to venglustat will be in compliance with all applicable national and local laws and regulations, including safety reporting obligations.

After safety data from Week 1/Day 1 to Week 12 visits of the first 5 participants of the primary population are reviewed and considered satisfactory by the DMC, enrollment of the secondary population will begin. In addition to the primary population, up to 20 participants in total are planned for the secondary population. An attempt will be made and first prioritized to enroll at least 1 participant (aged 2 years or older) in each of the following disorders: juvenile/adolescent late-onset GM2 gangliosidosis, GM1 gangliosidosis, Saposin C deficiency, Sialidosis Type 1, and juvenile/adult galactosialidosis (secondary population).

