Attempts should be made to perform all assessments in accordance with the approved protocol to the extent possible. In case this is not possible due to a temporary disruption caused by an emergency, focus should be given to assessments necessary to ensure the safety of participants and those important to preserving the main scientific value of the study.

- Postponement of visits is preferred to cancellation of visits, if possible. Visit window (V3 to V12) can be extended up to 3 months. In this case, IMP can be dispensed to the patient at the planned visit dates (via direct-to-patient) for a maximum duration of 6 months until V4, and thereafter for a maximum duration of 9 months without on-site visit, but with a follow-up by phone every 2 weeks. In general, no patient should continue IMP for >9 months without an on-site visit for safety assessments or without laboratory safety assessments being performed (eg, at the local practitioner). The safety laboratory parameters at least include hematology, biochemistry, urinalysis according to protocol.
- If Week 104 visit is delayed, the blinded treatment will be continued until Week 104 visit is performed.
- To reduce the time spent on-site during a study visit, the focus should be on the following safety assessments and if scheduled for the concerned visit (applicable to V3 to V12):
 - laboratory assessments (biochemistry, hematology and urinalysis)
 - urine pregnancy test

- ECG
- Physical (including vital signs), neurological and ophthalmological examinations (if required). For patients with existing cataracts at baseline, full eye exams with pupil dilation, photography and ARLNS evaluation at pre-specified visits should be carried out, to detect any worsening.

[REDACTED]
For efficacy assessments, should be prioritized to perform primary endpoints: CSF biomarker test (baseline and W104 only) and 9-HPT. [REDACTED]
[REDACTED].

For D1/W1 visit (V2), if it is within 2 weeks of V1, no need to redo the exams already performed at V1 except 9-HPT, 25-FWT and FARS Part III neurological examination and weight (for participants age <18). If D1/W1 visit (V2) is 2 to 4 weeks from the screening visit, assessments with the same request at screening and V2 may use the results at screening as baseline, except 9-HPT, 25-FWT, FARS Part III neurological examination, [REDACTED], chemistry, hematology, urinalysis and weight (for participants age <18).

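### SAP visit windows for the open-label extension have no OLE reference date, so a total shift of 92 days or more moves OLE visits one label on and leaves Week 208 outside every window

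*SAP*

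**What the plan says.** SAP 5.4 sets a single clock: "For all analyses, D1 will be defined as the reference date of the participant". It then adds: "For treated participant, the reference date will be the day of first IMP intake". Table 13 runs on that clock without a break to Week 208, whose window is "D1366 to D1547". No later window exists, and no second reference date is given for the OLE.

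Two rules make the windows binding for by-visit summaries: "A measurement (scheduled or unscheduled) will be used if it is available and measurement date is within the analysis window", and "If there is no measurement for a given parameter in an analysis window, data will be considered missing for the corresponding visit". CSF biomarkers and the neurological examination are exempt and are labelled by planned visit.

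The protocol lets the OLE start move. Under Protocol 4.1 (Period 3), participants who finished the primary period in the 3 months before local approval of amendment 4 "will have the option to enroll into the OLE when the OLE (amended protocol 4) is approved". The length of the OLE is fixed: "All participants will receive venglustat for 104 weeks in an open-label design". For emergencies, Protocol 10.11 (Appendix 11) states: "Visit window (V3 to V12) can be extended up to 3 months". It also keeps participants on blinded treatment until a delayed Week 104 visit takes place.

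SAP 3.1 recognises that a gap can occur. It ends the primary period at the later of the Week 104 visit and the day before the first OLE dose.

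**The concern.** Table 13 places the OLE visits as if the OLE always began the day after D728. When it begins later and still lasts 104 weeks, its visits move later, but the windows stay where they are. A large enough shift carries each visit into the next window and the last visit past the end of the table.

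The second-step analysis is meant to describe long-term results to Week 208. In the OLE, the schedule of activities has the 9-HPT, 25FWT and FARS only at W156 and W208, so losing or relabelling either one removes half of a participant's OLE functional data from its proper place. For laboratory data and vital signs, values taken after 26 weeks of OLE treatment would be summarised as Week 156. With about 57 primary and up to 20 secondary participants, a few such cases could visibly alter a by-visit summary.

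**Working it through.** **Reproducing Table 13.** Target day = 7 × week, giving D910, D1092, D1274 and D1456 for Weeks 130, 156, 182 and 208. Each upper limit is the midpoint to the next target, for example (910 + 1092)/2 = 1001. Week 208 ends at 1456 + 91 = 1547. All nine rows reproduce. Each OLE window runs from 90 days before target to 91 days after.

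**Inputs.** Let g be the total shift in days of the OLE start beyond D728, from a late Week 104 visit and/or a gap before the first OLE dose. Let v be the timing of a visit within its tolerance, from −14 to +14 days (Protocol 1.3). Assumption: OLE visits are scheduled from the OLE start.

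**Rule.** A visit falls on 7 × week + g + v. For shifts later than planned, it keeps its own label only if g + v ≤ 91.

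- g = 0 to 77: 77 + 14 = 91, so every visit is labelled correctly, even at the late end of its tolerance.
- g = 78 to 91: on-time visits are correct. A visit 14 days late fails from g = 78 (78 + 14 = 92), and one 7 days late from g = 85 (85 + 7 = 92).
- g = 92 to 105: on-time visits fail. Only visits held early enough stay in place.
- g = 106 or more: even a visit 14 days early fails (106 − 14 = 92).

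| Planned visit | Own window | On time, g = 91 | On time, g = 92 | Label at g = 92 |
|---|---|---|---|---|
| W130 | D820–D1001 | D1001 | D1002 | Week 156 |
| W156 | D1002–D1183 | D1183 | D1184 | Week 182 |
| W182 | D1184–D1365 | D1365 | D1366 | Week 208 |
| W208 | D1366–D1547 | D1547 | D1548 | none |

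**Can g reach 92?** Three months is about 90 to 92 days, so one full 3-month shift lands on the edge. Any time from approval to first OLE dose is added to it, as is a Week 104 visit held late within its ordinary 7-day tolerance (90 + 7 = 97). Two full shifts give about 92 + 92 = 184 days: W208 is then on D1640, outside every window, and W182 on D1458, reported as Week 208.

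**Functional tests at g = 92.** W156 data go to Week 182. W208 data have no window. The Week 156 and Week 208 windows then hold the W130 and W182 visits, at which these tests are not done, so both cells are empty.

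**Two visits in one window.** At g = 80, W130 held 14 days late is on D1004 and W156 on time is on D1172. Both lie in the Week 156 window. The SAP prefers the scheduled visit, but both are scheduled.

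**Week 104 itself.** A Week 104 visit 92 days late falls on 728 + 92 = D820 and would be labelled Week 130.

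**The case against.** The strongest reply is that the windows are wide enough. Each route to a late start is capped at 3 months, the windows absorb 91 days, and the documents show no participant with a shift of 78 days or more. The approval route was also transitional. This stands as a limit on the size of the problem. It does not remove it, because the approval route has no cap on the time from approval to first dose, and the two routes can add up.

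Second, neither document says that OLE visits are rescheduled from the first OLE dose. The schedule numbers weeks continuously from Day 1. This also stands. If visits kept their study-week dates the labels would be right, but a late starter's OLE would then be shorter than the stated 104 weeks. Rescheduling is the reading that fits that duration, but it is an inference.

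Third, time since first dose is a legitimate clock for change from baseline. At g = 92, W130 on D1002 is 90 days from the Week 156 target and 92 from its own, so the nearest-target label is not absurd. But that clock still provides no window for W208, and for participants first given placebo it does not measure time on venglustat.

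A reader might infer that any gap or delay mislabels visits, or that the Week 208 data are thrown away. The documents support neither. Shifts of up to 77 days change nothing, and an out-of-window value leaves only the by-visit summaries of windowed endpoints. The neurological examination, last and worst on-treatment values and the PCSA analyses do not depend on these labels. For laboratory data and vital signs at g = 92, the Week 208 cell is filled by the W182 visit, so it is mislabelled rather than empty.

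**Conclusion.** The point holds in limited form. Table 13 has no OLE anchor. Given scheduling from the OLE start, a total shift of 92 days or more (78 or more for visits 14 days late) moves W130, W156 and W182 one label on and leaves W208 outside every window.

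For these OLE visits the effect is confined to the second-step analysis, where efficacy is exploratory and descriptive. A reader should not extend it to the co-primary results: the 9-HPT model uses actual time, and CSF GM2 is labelled by planned visit. Nor is the Week 104 analysis wholly untouched. A Week 104 visit at D820 or later would leave its window, and time to meaningful worsening (SAP 3.2.2.4.3) takes its visits from Table 13.

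The number of participants affected is not given and could be zero. The change is still worth making, because a stated rule gives wrong labels in a situation the protocol permits.

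**What to change.** In SAP 5.4:

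- For OLE visits, count windows from the first OLE dose as OLE Day 1, with targets at OLE Days 182, 364, 546 and 728 and the same half-widths (−90/+91). With no shift, OLE Day 1 is D729, so these targets equal D910, D1092, D1274 and D1456 and nothing changes for participants who start on time. Alternatively, label OLE visits by planned visit, as is already done for CSF biomarkers and the neurological examination. Planned-visit labels also cover an OLE visit that is itself extended by 3 months, which anchored windows could still miss.
- Assign a delayed Week 104 visit held before the first OLE dose to Week 104, even if it falls after D819.
- State whether OLE visits after a gap are scheduled from Day 1 or from the OLE start.
- List each participant's days from the Week 104 visit to the first OLE dose, so that the number affected is visible.

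The cost is a short SAP edit, one derived variable and one listing. No new data are needed.

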5.5 APPENDIX 5 SCORING

5.5.1 Scoring of 9-HPT

The 9-HPT is a standardized, quantitative test of upper extremity (arm and hand) function. Both the dominant and non-dominant hands are tested twice (two consecutive trials of the dominant hand, followed immediately by two consecutive trials of the non-dominant hand). In brief, the participant is seated at a table with a small, shallow container holding the pegs and a block containing nine empty holes. On a start command when a stopwatch is started, the participant picks up the nine pegs one at a time as quickly as possible, puts them in the nine holes, and, once they are in the holes, removes them again as quickly as possible one at a time, replacing them into the shallow container. The total time to complete the task is recorded.

9-HPT will be scored according to Multiple Sclerosis Functional Composite (MSFC) instructions (2).

The two trials for each hand will be averaged, converted to the reciprocals of the mean times for each hand and then the two reciprocals will be averaged. The average of the two reciprocals will then be back-transformed in order to obtain the global 9-HPT on the original scale (in seconds).

Let D_1 and D_2 be the time to complete the 9-HPT for the dominant hand for the two trials and let ND_1 and ND_2 be the time to complete the 9-HPT for the non-dominant hand for the two trials. The overall 9-HPT is calculated as:

$$9HPT = \frac{2}{\left(\frac{2}{D_1 + D_2}\right) + \left(\frac{2}{ND_1 + ND_2}\right)}$$

In case a participant needs more than 5 minutes to complete in any trial (or was unable to complete trial due to physical limitations), the maximal time of 5 minutes (300 seconds) will be assigned.

Investigators will be reminded that missing data should be avoided. However, in case of missing data for other reason than inability to complete the test, missing data will be treated as follows:

- In case only 1 trial was done for a hand, the average of the two trials will be replaced by the time for the available trial.
- In case 9-HPT was assessed for only one hand, the overall 9-HPT will not be calculated and considered missing.

A higher value on the 9-HPT is indicative of higher disability.

